8 HANDLING OF MISSING VALUES

	Title: Statistical Analysis Plan
	Project #: IG1002 AMBAR
	Version: Final 1.0 Effective Date: 31July2018 Protocol Version: Version 5.0 Effective Date: Feb2018

Subjects with missing values for a given efficacy value at baseline of at the time point analyzed will be treated as missing rather than using imputed values.

The primary analysis will use a statistical methodology shown be robust in the presence of the type of missing data generally found in clinical trials, as described in Section 9.1.1.

Partial dates for adverse events and medications will be imputed to determine appropriate summarization, as follows:

Imputation of start dates (AE, CM) and assessments (LB, E.G., VS)

Missing Element	Rule
day, month, and year	
 No imputation will be done for completely missing dates
day, month	
 If available year = year of study treatment start date then 
 If stop date contains a full date and stop date is earlier than study treatment start date then set start date = 01JanYYYY Else set start date = study treatment start date. If available year > year of study treatment start date then 01JanYYYY If available year < year of study treatment start date then 01JulYYYY
day	
 If available month and year = month and year of study treatment start date then 
 If stop date contains a full date and stop date is earlier than study treatment start date then set start date= 01MONYYYY. Else set start date = study treatment start date. If available month and year > month and year of study treatment start date then 01MONYYYY If available month and year < month year of study treatment start date then 15MONYYYY

Imputation of end dates (AE, CM)

Missing Element	Rule (* = last treatment date plus 30 days not > (death date, cut-off date, withdrawal of consent date))
day, month, and year	
 Completely missing end dates (incl. ongoing events) will be imputed by the end date of the on-treatment period*

	Title: Statistical Analysis Plan
	Project #: IG1002 AMBAR
	Version: Final 1.0 Effective Date: 31July2018 Protocol Version: Version 5.0 Effective Date: Feb2018

Missing Element	Rule
	(* = last treatment date plus 30 days not > (death date, cut-off date, withdrawal of consent date))
day, month	• If partial end date contains year only, set end date = earliest of 31DecYYYY or end date of the on-treatment period *
day	• If partial end date contains month and year, set end date = earliest of last day of the month or end date of the on-treatment period*

Any AEs and ConMeds with partial/missing dates will be displayed as such in the data listings.

The extent of missing data will be reported to the FDA.

9 STATISTICAL METHODOLOGY AND STATISTICAL ANALYSES

9.1 STATISTICAL METHODS

9.1.1 Analyses for Continuous Efficacy end points

The primary efficacy end points, changes from baseline of the ADAS-Cog scores and changes from baseline in the ADCS-ADL inventory, will be analyzed over time using a mixed models repeated measures (MMRM) approach^{2,3,4}. The MMRM analysis will include fixed-effects factors for month (2, 6, 9, 12, and 14), treatment group, and the month-by-treatment interaction, with adjustment for age, disease severity and baseline ADAS-Cog score or the ADCS-ADL inventory, respectively. The model will include the subject as repeated factor. The covariance structure will be modeled using an “unstructured” (UN) which makes no assumptions about the within-subject variability. Other covariance structures may be considered if the “unstructured” model does not converge, such as AR(1) which assumes that observations close together (e.g., Months 6 and 9) are more highly correlated than observations further apart (e.g., Months 6 and 14). Although month 14 remains the primary time point, the month-by-treatment interaction allows for potential differences in the treatment effect at different time points. Pairwise contrasts will be constructed to compare the each dose group to the placebo group at each month specifically, where the comparison between each dose group and placebo at 14 months is the primary end point. All other comparisons will be regarded as secondary end points. Summary statistics will be provided for the actual values and for the change from baseline.

This MMRM approach can be implemented in SAS by a code similar to the following:

```
ODS output means =means diffs=diffs;
proc mixed data=dataset;
  class subject treatment visit;
  model change = age ADseverity baseline treatment visit
```

	Title: Statistical Analysis Plan
	Project #: IG1002 AMBAR
	Version: Final 1.0 Effective Date: 31July2018
	Protocol Version: Version 5.0 Effective Date: Feb2018

```

treatment*visit /ddfm=kr noint;
repeated time / sub = subject type = un;
lsmeans treatment*time /slice=time cl diff OM;
run; quit;

```

The difference from the control group will be obtained from the treatment * time interaction in the LS means statement (diffs dataset).

The analysis of ADAS-Cog change from baseline to month 14, and the ADCS-ADL change from baseline to month 14, will also be analyzed using analysis of covariance (ANCOVA) with treatment group as a fixed effect, and the corresponding baseline value, age and AD severity as a covariate. A similar model will be calculated also for all other point in time where the end points are assessed. This is considered a sensitivity analysis, and comparison of the results to the MMRM results allows for a qualitative assessment of the impact of missing data.

The two co-primary efficacy end points, change from baseline in the ADAS-Cog score and the change from baseline in the ADCS-ADL inventory score will also be analyzed by a random slope model. For this random slope model, time will be used as continuous variable and all observations (scheduled and unscheduled) will be used with the actual study day, rather than the slotted point in time. Subject and time will be used as random factor using an unstructured covariance matrix. Fixed effects in this model are the baseline value, age, AD severity, time, treatment and treatment*time interaction. The treatment effect will be analyzed by evaluating the treatment * time interaction term. This is considered as a second sensitivity analysis.

This random slope model can be implemented in SAS by a code similar to the following:

```

proc mixed data=data;
class subj;
model change = baseline age AD severity time trt time*trt/ s;
random intercept time / type=un subject=subj;
repeated / type=vc subject=subj;
run;

```

Possible drop-outs during the treatment phase will not only reduce the available sample size for the final analysis, drop-outs might not be at random and can, therefore, introduce bias to the analysis. Patients who experience less benefit from the treatment might have a higher probability to discontinue the treatment compared to patients who have a better outcome. Therefore, the possible impact of the drop-outs needs be evaluated. The baseline values and the changes from baseline in the ADAS-Cog score and the ADCS-ADL inventory score to the intermediate visit, month 6, month 9, and month 12 will be compared descriptively for each treatment group between the patients who completed the study and patients who prematurely dropped out (Patients who did not complete the final assessment at month 14). Possible differences in the response to the treatment and the

	Title: Statistical Analysis Plan
	Project #: IG1002 AMBAR
	Version: Final 1.0 Effective Date: 31July2018
	Protocol Version: Version 5.0 Effective Date: Feb2018

patient characteristics between the patients who completed the study and the patients who prematurely dropped out may be further investigated in an explorative manner, if needed.

Due to the added complexity of the MMRM approach, all other efficacy end points with baseline and post-baseline data will analyze change from baseline to that specific time point using analysis of covariance (ANCOVA) with treatment group as a fixed effect, and the corresponding baseline value, age and AD severity as a covariate. Expanded use of MMRM into secondary analyses may be considered if the results for the MMRM and ANCOVA methodologies for the primary analysis are qualitatively different. Summary statistics will be provided for the actual values and for the changes from baseline.

If the assumption of normality is significantly violated, a non-parametric analysis will be used. Specifically, if the Wilk-Shapiro test for normality of the residuals is significant at the 0.01 level, a rank ANCOVA procedure will be applied, as follows. The standardized ranks for both covariate and the response variable will be produced for each stratum. Then linear regression models will be performed on ranked data by stratum to generate the residuals. Finally the stratified mean score test using the value of the residuals as scores will compare the treatment groups using the Cochran-Mantel-Haenszel procedure⁵.

This statistical test will be 2-tailed using $\alpha=0.05$, with adjustment for multiple comparisons as described in Section 4.2.

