4.2 STATISTICAL DECISION RULES

The statistical tests will be performed with a 5% significance level and will be two-sided. In addition to the tests, two-sided 95% confidence intervals (95% CI) will be reported.

Because the end points are co-primaries, both must be statistically significant for the study to provide evidence of efficacy. Therefore, no multiplicity adjustment is needed to adjust for the co-primary end points. However, to account for the three dose group comparisons to placebo and to maintain the overall significance level of 0.05, adjustment for α will be made for multiple dose groups according to the Hochberg¹ procedure. The

	Title: Statistical Analysis Plan
	Project #: IG1002 AMBAR
	Version: Final 1.0 Effective Date: 31July2018
	Protocol Version: Version 5.0 Effective Date: Feb2018

Hochberg procedure will be implemented as follows: For each end point, the three dose group comparisons versus placebo will be ordered according to the p-value from the largest to the smallest. If the largest p-value is < 0.05 then all comparisons to placebo will be declared significant. Otherwise, if the second largest p-value is < 0.025 (0.05/2) then this dose and all doses with smaller p-values will be declared significant. Otherwise, if the smallest p-value is < 0.0167 (0.05/3) then this dose will be declared significant. Otherwise, no dose is considered significantly different from placebo. This procedure has been demonstrated to control the overall Type I error at 0.05. Both co-primary end points must be significant at a given dose to provide evidence of efficacy for that dose.

Specifically, the null hypothesis for all inferential analyses, including the primary end points, is that all three treatment groups are equal to placebo. Specific doses will be considered different from placebo if statistically significant following the Hochberg procedure described above. The study is considered positive if at least one dose group differs from placebo in both of the co-primary analyses. Subsequently, secondary end points are considered positive if at least one dose group differs from placebo.

A supportive analysis will be performed in per protocol analysis set for each of the co-primary efficacy end points applying the same respective methodologies, but without adjusting for Type I error.

[figure not shown]

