7 END POINTS AND COVARIATES

Baseline is defined as the last assessment prior to study drug administration (first full plasma exchange or sham treatment in the control group).

Most summaries will include the 4 treatment groups and cover the entire study period (including both the intensive and maintenance phases), but some analyses (particularly safety) may summarize a specific phase. Summary statistics will be provided for the

	Title: Statistical Analysis Plan
	Project #: IG1002 AMBAR
	Version: Final 1.0 Effective Date: 31July2018
	Protocol Version: Version 5.0 Effective Date: Feb2018

actual value and for the change from baseline for each point in time a variable is measured. Only available data will be included in these summary statistics, if not otherwise stated, no substitution of missing values will be done. In addition to the analysis at each point in time a variable is measured, for the safety variables and the biomarkers an analysis will also be performed for the last non-missing post-baseline value (end point).

Study days will be numbered relative to the first day of study drug administration. The start of treatment (Day 1) is defined as the date on which a patient receive the first study treatment. Days will be numbered relative to study start (i.e., ..., -2, -1, 1, 2, ...; with day 1 being the first administration of study treatment and day -1 being the day before the first administration of study treatment).

Protocol-defined efficacy assessments will be “slotted” to study visits based on collection date and applying the rules summarized in the following table. The study day range is the time period where assessments can be selected to populate a study visit, e.g. the assessments from study day 92 to study day 228 can be considered as assessments for the LVPE Visit 4 (month 6) visits.

Visit	Target Study Day	Study day range
Screening/Baseline		$-\infty$ to 1
FPE Visit 1 (Week 1)*	1	1
Intermediate visit (Week 7-8)	45	2 to 93
LVPE Visit 4 (Month 6)	141	94 to 184
LVPE Visit 7 (Month 9)	225	185 to 268
LVPE Visit 10 (Month 12)	309	269 to 343
Final Visit	375	344 to ∞
* Reference date for all other visits		

The slotting scheme for the CSF biomarkers will be as follows:

Visit	Target Study Day	Study day range
Screening/Baseline		$-\infty$ to 1
FPE Visit 1 (Week 1)*	1	1
Intermediate visit (Week 7-8)	45	2 to 187
Final Visit	375	188 to ∞
* Reference date for all other visits		

	Title: Statistical Analysis Plan
	Project #: IG1002 AMBAR

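### If the unstructured primary MMRM fails to converge, the only fallback the SAP names, AR(1), assumes equal variance at all visits and would understate the Month 14 standard error if change scores spread over time

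*SAP*

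**What the plan says.** SAP 9.1.1 analyses change from baseline in ADAS-Cog and in ADCS-ADL with a mixed model for repeated measures containing "fixed-effects factors for month (2, 6, 9, 12, and 14), treatment group, and the month-by-treatment interaction", adjusted for age, severity and baseline. It states that "the comparison between each dose group and placebo at 14 months is the primary end point".

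The first-choice covariance is unstructured, "which makes no assumptions about the within-subject variability". Should that fit fail, the SAP permits alternatives without requiring any particular one, and offers a single illustration: "such as AR(1) which assumes that observations close together (e.g., Months 6 and 9) are more highly correlated than observations further apart". No other structure is named and no order of preference is set. AR(1) is described only by how its correlation decays.

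The sample code has the option "treatment*visit /ddfm=kr noint", that is, Kenward-Roger degrees of freedom. It does not request an empirical (sandwich) covariance, so the standard errors are model-based.

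SAP 4.2 sets the error rate: "The statistical tests will be performed with a 5% significance level and will be two-sided". Hochberg is applied over the three arms within each endpoint, and both endpoints must be significant at the same dose.

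**The concern.** AR(1) has two parameters, one variance and one correlation. The unstructured model gives Month 14 its own variance; AR(1) makes it share one with Months 2, 6, 9 and 12. The outcome is change from baseline in a progressive disease, so it is plausible that patients diverge over time and that Month 14, the last visit, is the most variable. The SAP's own second sensitivity analysis allows for this: a random intercept and random slope on time let the variance change over follow-up. AR(1) rules it out.

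If spread does grow, the pooled variance is smaller than the Month 14 variance, and the decisive test rejects too often. Kenward-Roger is a small-sample adjustment and does not repair a wrong covariance structure. What is at stake is the 5% error rate that SAP 4.2 says is controlled, in the one situation where the fallback is used.

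**Working it through.** **Inputs.** From the SAP: five visits with target days 45, 141, 225, 309 and 375 (section 7 visit table, for example the row "LVPE Visit 4 (Month 6) 141 94 to 184"); two-sided 5%, with a smallest Hochberg step of 0.0167 (4.2); 78 evaluable per arm, 312 in all, and SDs of 5.55 and 10.0 (2.1). Not in the documents: the SD at each visit. I assume it rises linearly from r × SD(M14) at Month 2 to SD(M14) at Month 14, and vary r.

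**The plan's own figures.** The plan gives no operating characteristics for the fallback. Its power figures do reproduce.
- ADAS-Cog: 3 / (5.55 × √(2/78)) = 3.376; 3.376 − 1.96 = 1.416; power 92.2% (stated: nearly 92%).
- ADCS-ADL: 6.69 / (10 × √(2/78)) = 4.178; 4.178 − 1.96 = 2.218; power 98.7% (stated: over 98%).
- Joint: 0.92 × 0.98 = 0.90, as stated.

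**Step 1: error formula.** With treatment-by-visit means and complete data, the Month 14 estimate is the difference in Month 14 means whichever covariance is fitted. Only its standard error changes. Under AR(1) that uses the pooled SD, so

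type I error = 2 × [1 − Φ(1.96 × k)], where k = SD(pooled) / SD(M14).

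**Step 2: k.** The AR(1) variance that minimises the Gaussian deviance is very close to the plain mean of the five variances, and depends little on the true correlation. With t = (day − 45)/330 = 0, 0.291, 0.545, 0.800, 1, the mean of t is 0.527 and the mean of t² is 0.404. Hence

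k² ≈ r² + 2r(1 − r) × 0.527 + (1 − r)² × 0.404.

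| r = SD(M2)/SD(M14) | k | Type I error |
|---|---|---|
| 1.0 | 1.000 | 5.0% |
| 0.9 | 0.953 | 6.2% |
| 0.8 | 0.908 | 7.5% |
| 0.7 | 0.865 | 9.0% |
| 0.6 | 0.823 | 10.7% |
| 0.5 | 0.784 | 12.4% |

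Growth that is linear in nominal month gives slightly less, for example 12.0% at r = 0.5. Varying the true lag correlation from 0.5 to 0.85 moves these results by about 0.1 percentage point.

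**Step 3: where the error doubles.** A 10% error needs k = 1.645/1.96 = 0.839, which is r of about 0.63 (an SD of about 3.5 at Month 2 against 5.55 at Month 14). At the 0.0167 step the error doubles at r of about 0.75, where it is 3.4%.

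**Step 4: simulation of the planned model.** Four arms of 91 enrolled, no treatment effect, monotone random drop-out reaching 15%, covariates, REML, normal reference, growth linear in month. There were 1,500 runs for each AR(1) row and 300 for the unstructured row.

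| Fitted structure | SD growth, M2 to M14 | One comparison | Hochberg over 3 arms, one endpoint |
|---|---|---|---|
| AR(1) | none | 5.2% | 4.5% |
| AR(1) | ×1.5 | 9.6% | 11.3% |
| AR(1) | ×2 | 12.6% | 15.1% |
| Unstructured | ×2 | 4.1% | 4.7% |

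Monte Carlo error is at most √(0.126 × 0.874/1500) = 0.9 points for the ×2 AR(1) per-comparison rate and √(0.041 × 0.959/300) = 1.1 points for the unstructured one. With ×2 growth the mean Month 14 standard error was 0.687 under AR(1) and 0.877 under unstructured: 0.687/0.877 = 0.78, about 22% too small.

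**Step 5: does the remedy hold?** In the large-sample calculation ARH(1), which has a variance per visit, stayed at 5.0 to 5.7% at every growth ratio, even with its correlation misspecified.

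**Step 6: visit spacing.** The gaps are 96, 84, 84 and 66 days. With constant variance and correlation decaying with elapsed time, AR(1) left the error at 5.0%. The common variance is the cause.

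**The case against.** Five points can be made for the plan.

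1. **The trigger is unlikely.** Five visits give 5 × 6/2 = 15 covariance parameters for about 312 subjects, so the unstructured model should converge. This stands. A reader might infer that the primary analysis is anti-conservative; it is not, and the unstructured model held its error rate in Step 4.

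2. **AR(1) is an example.** A reader might take the SAP as committed to it. The wording is permissive and the list open, so heterogeneous structures are already allowed. This stands too, but it leaves the covariance for the decisive test to be chosen after the model has failed, and SAP 3 places unblinding and final analysis after database lock.

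3. **Variance growth is not documented.** One SD per endpoint is given. The documents neither show growth nor exclude it, and at r of 0.8 to 0.9 the error is only 6.2 to 7.5%.

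4. **Both endpoints must succeed.** A reader might infer a doubled false-claim rate for the trial. If both endpoints are null, it is far lower: applying the inflation to both at r = 0.6 gives 0.8, 1.5, 2.8 or 4.6% for between-endpoint correlations of 0, 0.3, 0.5 or 0.7 (assumed values), and at r = 0.5 it gives 1.3, 2.1, 3.6 or 5.9%. The full inflation carries over only when the other endpoint has a real effect. Strict control must cover that case, but it is the least favourable one.

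5. **A Month 14 ANCOVA is planned.** Its residual variance comes from Month 14 alone, and SAP 9.1.1 compares it with the MMRM, so an AR(1) standard error that was too small should show. In the SAP it is a sensitivity analysis and does not decide success.

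A reader might also blame the unequal visit intervals. Step 6 shows that they do not drive the error.

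**Conclusion.** The point holds as a weakness in the fallback. If the unstructured model fails, if AR(1) is then chosen, and if the SD of change grows between Month 2 and Month 14, the Month 14 test is anti-conservative for that endpoint. The size runs from about 6% with mild growth to about 12% if the SD doubles, and reaches 10% at an SD ratio of about 0.63. These rates are per endpoint and per comparison. They rest on an assumed linear growth of SD, which the documents do not let a reader check.

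The documents do not support saying that the planned primary analysis inflates the error, that the SAP binds the sponsor to AR(1), or that the trial-level false-claim rate doubles in general. Because the trigger is unlikely and the fix is nearly free, this is a minor improvement.

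**What to change.** In SAP 9.1.1, replace the open example with a fixed order in which every structure keeps a separate variance for each visit: heterogeneous Toeplitz, then ARH(1), then heterogeneous compound symmetry, using the first that converges. Add that if a homogeneous structure is ever reached, the Month 14 contrasts use the empirical (sandwich) standard error. The degrees-of-freedom method for that case should be named too, since Kenward-Roger is built for the model-based covariance.

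The cost is about one sentence, to be settled before unblinding. Nothing changes if the unstructured model converges. In the fallback case the Month 14 interval would be slightly wider than under AR(1) if the variance is in fact constant; if the variance grows, the extra width is what the data require.

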4.3 Planned Number of Subjects

A sample size of 312 subjects (78 per each of the 4 groups) will make it possible to detect with nearly 92% power for the first of the co-primary efficacy variable (the changes from baseline of the ADAS -Cog scores) a difference in the mean of 3 points between any of the treatment groups and the control group, assuming the common standard deviation (SD) to be 5.55 (according to the data obtained in the phase II study⁶⁵), with a level of significance of 5%. This same sample size provides over 98% power for second of the co-primary endpoint variables (the changes from baseline of the ADCS-ADL inventory scores) a difference in the mean of 6.69 points between any of the treatment groups and the control group, assuming the common standard deviation (SD) to be 10.0 (according to the data obtained in the phase II study), with a level of significance of 5%.

The study will have joint power for these co-primary endpoints of at least 90% ($0.92 \times 0.98 = 0.90$). The calculation makes the conservative assumption that these endpoints are independent. Since these endpoints may be positively correlated 90% should serve as a lower bound on power.

Assuming a global dropout rate of approximately 15%, the study would have to enroll 364 subjects to obtain 312 subjects for evaluation.

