7.4 COVARIATES

For the analysis of the cognitive, functional, and neuropsychiatric scores, the corresponding baseline scores, age, and AD severity will be used as a covariate for each change from baseline model. Disease severity will be defined by the baseline MMSE score as follows:

- MMSE 18 – 21 points
- MMSE 22 – 26 points

An exception is the model for the changes from baseline for the MMSE. This model will only be adjusted for age and the baseline value. Also the models for the subgroups by severity will only be adjusted for age and baseline value.

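### The primary MMRM holds one baseline slope for Months 2 to 14; a baseline-by-visit term costs four degrees of freedom and may tighten the Month 14 contrast

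*SAP*

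**What the plan says.** The prose of SAP 9.1.1 gives the primary model for both co-primaries factors for month, treatment and their interaction, an unstructured covariance, and adjustment for age, disease severity and the matching baseline score. The sample code has "model change = age ADseverity baseline treatment visit", and treatment by visit is its only interaction. The code is offered as an example, but the prose and the table in SAP 9.2.5 contain no baseline-by-visit term either.

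On the severity covariate, SAP 7.4 states: "Disease severity will be defined by the baseline MMSE score as follows". It then lists two groups, 18–21 and 22–26.

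SAP 9.1.1 keeps a Month 14 ANCOVA as a sensitivity analysis and uses its agreement with the MMRM to judge how much missing data matter. It may extend MMRM to secondary endpoints if the two disagree. In Protocol 10.2.2 a baseline-adjusted ANCOVA was the primary analysis.

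Protocol 4.3 rests the sample size on SDs of change from the phase II study and does not mention covariate adjustment.

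**The concern.** The model lets the treatment effect and the covariance differ at every visit, yet fixes the relation between baseline and change at one value from Month 2 to Month 14. The SAP gives no reason for this. The relation could plausibly change over a year. If it does, the common slope is a compromise that fits Month 14 imperfectly, and the misfit goes into the Month 14 residual variance. Three things are then at stake:

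- the width of the Month 14 interval;
- the estimate itself, if drop-out depends on baseline in a way that differs between arms;
- the meaning of the MMRM–ANCOVA comparison. A Month 14 ANCOVA fits its own Month 14 slope and the planned MMRM does not, so the two differ in more than their handling of missing data.

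**Working it through.** **1. The plan's own figures.** Inputs from Protocol 4.3: "A sample size of 312 subjects (78 per each of the 4 groups"; "a difference in the mean of 3 points between any of the treatment groups and the control group"; an ADAS-Cog SD of 5.55. For ADCS-ADL they are 6.69 points and SD 10.0. Alpha is 5% two-sided (SAP 4.2: "The statistical tests will be performed with a 5% significance level and will be two-sided"). Power = Φ(δ / (σ√(2/n)) − 1.96).

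- ADAS-Cog: 3 / (5.55 × √(2/78)) = 3.376; Φ(1.416) = 92.2%. The protocol says "with nearly 92% power for the first of the co-primary efficacy variable".
- ADCS-ADL: 6.69 / (10 × √(2/78)) = 4.178; Φ(2.218) = 98.7%. The protocol says over 98%.
- Joint power under independence: 0.922 × 0.987 ≈ 0.91, against at least 90% stated.

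The stated figures reproduce. They use an SD of change with no credit for covariates, so the baseline term does not enter them.

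**2. Cost of a common slope, closed form.** With complete data, the Month 14 variance relative to a model with month-specific slopes is about 1 + (b14 − bc)² × SD_base² / SD_res². Here b14 is the Month 14 slope and bc the common slope that the model fits. SD_base and the slopes are assumptions; 5.55 stands in for SD_res.

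- Equal slopes: b14 − bc = 0, ratio 1.
- SD_base 7, deviation 0.05: 1 + (0.35)² / 30.80 = 1.004.
- SD_base 9, deviation 0.15: 1 + (1.35)² / 30.80 = 1.059, which would take 92.2% power to 90.7%.

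Over all settings tried (Month 2-to-14 slope difference 0.05 to 0.3, SD_base 7 to 9, several residual structures) the excess ran from 0.1% to 15%. If 5.55 were the SD under the correct model, power would fall from 92.2% to between 92.1% and 88.1%.

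**3. Simulation of the MMRM.** Settings: 91 per arm in four arms, five visits, 15% random monotone drop-out, unstructured covariance, baseline SD 8, residual SD rising from 4 to 5.55, 150 replicates per row. An assumed MMSE effect (0, 0.10, 0.15, 0.20 SD) was raised together with the slope difference, so the rows reflect both. Power is for one ADAS-Cog comparison before the Hochberg step.

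| Slope difference | SE, plan | SE, with `baseline*visit` | Ratio | Power |
|---|---|---|---|---|
| 0 | 0.8609 | 0.8608 | 1.000 | 93.6% → 93.6% |
| 0.1 | 0.8758 | 0.8670 | 0.990 | 92.9% → 93.3% |
| 0.2 | 0.9065 | 0.8741 | 0.964 | 91.1% → 93.0% |
| 0.3 | 0.9344 | 0.8696 | 0.931 | 89.4% → 93.2% |

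The spread of the estimates over replicates moved the same way but less: ratios 0.789/0.785 = 1.005, 0.828/0.834 = 0.993, 0.951/0.970 = 0.980 and 0.883/0.933 = 0.946. With 150 replicates these are rough. Mean estimates were close to the true 3 points under both models.

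**4. Two MMSE groups.** If MMSE were uniform on 18–26, the groups have means 19.5 and 24.0 and shares 4/9 and 5/9. The between-group variance is (4/9)(5/9)(4.5)² = 5.0 against a total of 60/9 = 6.67, so the cut keeps 75% of the linear information (66–75% over the shapes tried). Baseline ADAS-Cog is already in the model, however. In the simulation, replacing the groups by continuous MMSE alone gave SE ratios of 1.000, 1.000, 0.999 and 0.997.

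**5. Drop-out that depends on baseline.** Separate simulations used 91 per arm and assumed parameters.

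- Drop-out related to baseline equally in both arms: no meaningful shift. One run gave −2.96 (Monte Carlo SE 0.03) against a truth of −3.
- Drop-out related to baseline differently by arm: the planned estimate differed from the `baseline*visit` estimate by 0.07–0.08, 0.12–0.20 and 0.19–0.25 points at slope differences of 0.1, 0.2 and 0.3. A further run with strongly different drop-out gave a bias of about 0.27.

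**The case against.** The strongest reply is that the premise is not documented. Neither document gives a slope by month, a baseline SD or an MMSE correlation, and with equal slopes the loss is exactly zero. That stands, and it is why the size is given as a range that includes zero. It is also true that the prespecified Month 14 ANCOVA would expose a serious slope problem. But it does not narrow the primary interval, and it cannot separate the slope restriction from missing data.

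A reader might infer more than the documents support:

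- *That a definite number of patients is being wasted, or that the stated power is wrong.* The patient equivalent depends wholly on unknown slopes, and the power calculation took no credit for covariates.
- *That the MMRM is biased whenever drop-out depends on baseline.* Randomisation balances baseline, so the shift needs baseline-dependent drop-out that differs by arm. SAP 9.1.1 allows that drop-out may not be random, but neither document says that it will differ in this way.
- *That cutting MMSE matters as much as the missing interaction.* In simulation it changed the SE by at most about 0.3%.
- *That the same percentages apply to ADCS-ADL.* Nothing was computed for it.

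**Conclusion.** The restriction is real and appears in the prose, the code and the table. It is a missed, nearly free improvement, not an error in the plan or a threat to the type I error rate. For ADAS-Cog, `baseline*visit` would reduce the Month 14 standard error by about 0 to 7%, assuming a baseline SD of 8 and a slope difference of 0 to 0.3. The Month 14 estimate could move by about 0.1 to 0.3 points, but only under arm-differential, baseline-dependent drop-out. The point about interpretation needs no assumed numbers: as planned, the MMRM and the ANCOVA differ both in the baseline slope and in the handling of missing data.

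**What to change.** Before database lock, to which SAP 3 ties unblinding, add `baseline*visit` to the MODEL statement, the prose of SAP 9.1.1 and the primary rows of the table in SAP 9.2.5, for ADAS-Cog and ADCS-ADL alike. Five visit-specific slopes replace one, which costs four degrees of freedom and needs no new data or visits.

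Continuous baseline MMSE in place of the two groups is optional: it costs no extra degrees of freedom, but little gain should be expected. If it is adopted, keep the 18–21 and 22–26 groups for the severity subgroups and for any stratified rank-ANCOVA fallback, which needs a categorical stratum.
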